## V. *Data Collection Procedures*

**Procedures.** Following phone screen, eligible participants will be invited to the Psychology Clinical Neuroscience Center (PCNC) for the baseline session, which includes being breathalyzed to ensure a breath alcohol concentration (BAC) of 0.0, pregnancy testing for fertile female participants, providing informed consent, completing a battery of self-report and behavioral measures, baseline EEG, and baseline stimulation session. Participants who have a BAC > 0.0 will be rescheduled, given snacks and water until their BAC is reduced to < 0.04 in accordance with NIAAA guidelines, and will be provided a taxi voucher. Participants will take part in the intervention for 8 two and a half hour sessions up to 8 weeks. At each 150-minute session, participants will undergo 30 minutes of initial assessment and verification of session eligibility (e.g., breathalyzer, withdrawal assessment, pregnancy tests, and self-report), 30 minutes of tDCS during a guided meditation practice followed by 90 minutes of MBRP session content. The overarching goal of the meditation is to help participants obtain greater mental clarity through training attention and awareness, decreasing emotional reactivity, and improving general well-being. All study participants will be assigned to the MBRP condition. All tDCS sessions will be double blinded with active and sham tDCS participants within all groups. Pilot testing of this protocol has demonstrated feasibility of combining active and sham tDCS within a single group, while maintaining the blind.

**Measures.** Table 1 provides the assessment schedule for the proposed study. Consistent with the Secondary Aim to understand the mechanisms of behavior change at multiple levels of analysis, we have included self-report and behavioral assessments of inhibitory control (NIH Cognition Toolbox, UPPS Impulsive Behavior Scale, Stop Signal Task), cue reactivity and craving (Penn Alcohol Craving Scale, Cue Reactivity), and negative affect (NIH Emotions Toolbox, Negative Affect Reactivity). We have also included a blinding questionnaire to assess the degree to which individuals were blinded to the active versus sham tDCS randomization condition. Breathalyzer tests will be conducted prior to all interviews. Participants who have a BAC > 0.0 will be rescheduled, given snacks and water until their BAC is reduced to < 0.04 in accordance with NIAAA guidelines, and will be provided a taxi voucher.

During each assessment period (i.e. baseline, end-of-treatment, and 2-month post-treatment follow-ups), self-report measures, and the EEG sessions will occur within one week of the self-report assessment on separate days or on a single day with a break between assessments. All assessments (behavioral, EEG) and treatment sessions will take place in the PCNC. The PCNC has three private assessment rooms to conduct behavioral assessments, as well as an EEG preparation room and shielded acquisition room.

Measure	Description/Purpose	Follow-up		
		Baseline	Post	2-Mo
Locator Form	Contact information for scheduling appointments	X	X	
Edinburgh Handedness scale	Right handedness (inclusion criteria)	X		
Electroencephalography (EEG)	Electrical activity of the brain	X	X	
Demographic form	Age, gender, education, ethnicity	X		
	Marital & employment status, income	X	X	X
Drinking History Questionnaire	Drinking history: onset, prior/current treatment	X	X	X
Form 90	Alcohol & illicit drug use, treatment seeking & AA	X	X	X
Structured Clinical Interview for DSM-IV modified for DSM-5 to include craving item	AUD diagnosis/comorbid SUD diagnoses	X	X	X
Short Inventory of Problems	Brief measure of alcohol-related problems	X	X	X
Penn Alcohol Craving Scale (PACS)	Self-reported craving for alcohol	X	X	X
Impaired Control Scale	Self-reported craving, difficulty controlling craving	X	X	X
International Affective Pictures Series (IAPS)	Behavioral measure cue/negative affect reactivity	X	X	X
UPPS Impulsive Behavior Scale	Urgency, lack of planning, perseveration	X	X	X
Stop Signal Task	Behavioral measure of cognitive control	X	X	X
Mindfulness daily practice tracking sheet	Current mindfulness practices	X	X	X
Breath Counting Tool	Behavioral measure of mindfulness	X	X	X
Toronto Mindfulness Scale	"State" mindfulness	X	X	X
NIH Emotions Toolbox	Social relationships, negative affect, and stress	X	X	X
NIH Cognition Toolbox	Executive function (shifting/attention), memory	X	X	X
Avoidance and Inflexibility Scale	Behavioral avoidance	X	X	X
Regulatory Flexibility Scale	Coping flexibility	X	X	X
Monetary Choice Questionnaire	Delay discounting	X	X	X
Treatment History Form	Assess ongoing treatment and prior/ongoing experience with meditation	X	X	X
Treatment Goals Form	Assess current treatment goal (e.g., controlled drinking, abstinence)	X	X	X
Applied Mindfulness Process Scale	Assess mindfulness skills learned during intervention		X	X
Clinical Institute Withdrawal Assessment of Alcohol Scale, Revised	Measure of current alcohol withdrawal symptoms	X		
Blinding Questionnaire	One question assessing knowledge of condition		X	

**Primary Drinking Outcome.** The *Form 90* (Miller, 1996) is a semi-structured interview that gathers daily calendar-based alcohol and illicit drug use data. A 2-month assessment window will be used at each of the time-points. The *Form 90* will be used to derive estimates of the primary outcome: drinks per drinking day. The *Form 90* has demonstrated reliability in the collection of alcohol and drug use data (Maisto, Conigliaro, Gordon, McGinnis, & Justice, 2008; Sobell, Brown, Leo, & Sobell, 1996).

**Weekly During Treatment Measures.** An abbreviated assessment battery will be administered weekly during treatment to assess state mindfulness (Toronto Mindfulness Scale (Lau et al., 2006)), mindfulness practice in the prior week, craving (PACS; Flannery Volpicelli, & Pettinati, 1999), negative urgency and lack of planning items from the UPPS (Littlefield et al., 2015; Whiteside & Lynam, 2001), and negative affect (Short Forms of Anger, Sadness, Stress from NIH Emotions Toolbox; Salsman et al., 2013).

**Behavioral Tasks.** All behavioral tasks will be completed via computer during EEG to provide a measure of electrical brain activity during rest and completion of the tasks. To examine inhibitory control, we will use a *Stop Signal Task* (Logan, Van Zandt, Verbruggen, & Wagenmakers, 2014) in which participants make left-right judgments of the directionality of an arrow presented on the screen. For each trial, a circle will appear for 500 ms, followed by a left or right-pointing arrow for up to 1 second, and between 500 ms and 2500 ms jittered inter-trial interval to reduce anticipatory responses. Approximately 25% of trials will be "stop trials" with a tone played to signal participants to inhibit the

current response. This timing of the tone is dynamically adjusted to ensure successful inhibition on approximately 50% of trials. There will be 240 trials across six blocks (~10 minutes) (Wessel & Aron, 2015). To measure cue-elicited responses to alcohol, we will use a visual cue presentation task. Following the designs of (Bartholow, Lust, & Tragesser, 2010; Myrick et al., 2008; Vollstädt-Klein et al., 2010), participants will view pictures of alcohol containing beverages and neutral pictures from the *International Affective Pictures Series (IAPS)* (Lang, Bradley, & Cuthbert, 1999) and from the web. Alcohol and neutral pictures will be matched for color and complexity as well as other potentially important confounds (e.g., presence of people). We will examine responses to approximately 100 trials each of alcohol pictures and control pictures in a mixed event design (~15 minutes), in order to reduce predictability of the picture type. To assess negative affect reactivity, participants will complete an anticipatory reactivity task in which arbitrary cues (circle or square) predict either neutral or aversive pictures from the *IAPS* (Lang et al., 1999). Participants will be instructed to press a button as fast as possible when the white square appears. If a response threshold is met, participants will see the neutral pictures or be able to avoid viewing the negative pictures. Importantly, the response threshold is dynamically determined throughout the task to ensure success/failure on approximately 66% of neutral/negative trials. Analyses will focus on the anticipatory period between the cue and picture. We are interested in examining differences between anticipation and experience of negative compared to neutral pictures. We will use 150 trials per cue condition to ensure an adequate signal to noise ratio (Brown, Goodman, & Inzlicht, 2013) (~20 minutes). Finally, we will include a novel *breath-counting task* that has been validated as a behavioral measure of mindfulness (Levinson, Stoll, Kindy, Merry, & Davidson, 2014). Participants will be instructed to count breaths from 1 to 9, pressing one button for breaths 1-8 and pressing another button on the 9th breath. The counting will be interrupted at random by three question probes assessing awareness and current breath count. There will be 12 question probes every 60-120 seconds (~18 minutes).

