**MBRP + tDCS Sessions (2 hour treatment groups + 30 minutes for initial assessments, breathalyzer, pregnancy tests, and withdrawal assessments).** Following the baseline session, participants will begin a series of weekly or twice weekly group MBRP + tDCS intervention sessions for up to eight weeks at the PCNC. To maximize the availability of groups and to accommodate various therapist schedules we will run groups either twice per week for four weeks or once per week for eight weeks. All participants will receive up to 8 two hour sessions of MBRP + tDCS, regardless of the group schedule.

At the beginning of each session the subject will be asked to complete a baseline mood assessment, all participants will be breathalyzed, and fertile female participants will be asked to complete a pregnancy test. Women who are pregnant will not be allowed to complete the study and will be told in private of their pregnancy status. Participants who have a BAC > 0.0 will be rescheduled, given snacks and water until their BAC is reduced to < 0.04 in accordance with NIAAA guidelines, and will be provided a taxi voucher. We will also assess all participants for potential alcohol withdrawal at the time of each tDCS session. If participants show significant signs of withdrawal and/or have a score of 8 or greater on the Clinical Institute Withdrawal of Alcohol Assessment Scale (CIWA), then the research assistant will recommend the subject go to the UNM Hospital for further assessment. Our previous studies with more severely dependent individuals occasionally encountered patients with severe withdrawal, and this protocol was used successfully without any adverse consequences. Subjects with CIWA scores of 8 or greater at any session will be excluded from the research study. These aspects of the study will take approximately 30 minutes to complete.

Subjects will then receive 30 minutes of either active or sham tDCS stimulation, depending on their group assignment. A sensation questionnaire will be administered after 5 minutes of tDCS, 15 minutes, and 25 minutes of tDCS. At the end of tDCS stimulation participants will be asked a few questions regarding their mood and mental state to make sure that they have no lingering effects of the stimulation. After tDCS stimulation the remaining time will be used for MBRP session content (described below).

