**Post-Treatment Assessment (up to 5 hours).** After completing the MBRP + tDCS sessions (i.e., up to two weeks after final tDCS/mindfulness session), participants will complete the assessments listed in Table 1 at the PCNC.

**Follow-Up Assessment (up to 2 hours).** At 2 months following completion of MBRP+tDCS, participants will complete the assessments listed in Table 1, with the exception of EEG, at the PCNC.

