## II. *Data Analysis/Statistical Considerations*

**Power analysis and sample size considerations.** We conducted power analyses using effect sizes from a pilot study ( $d=0.64$  and  $d=0.43$  on drinks per drinking day at post- and 2-month follow-up). With desired power  $>0.80$ , a two-tailed  $\alpha < 0.05$ , and three time-points, we will need 70 participants to detect a medium effect of active tDCS + MBRP vs. sham tDCS + MBRP on drinks per drinking day at follow-up. For mediation analyses we will need 74 participants to detect a medium effect. Attrition of 15% is anticipated based on our pilot tDCS study and thus we propose to recruit  $n=86$  participants to allow for some attrition. We anticipate screening up to 350 participants in order to recruit a sample of 86 participants.

**Data Analyses and Missing Data.** The primary study aim is to test the overall efficacy of the active tDCS + MBRP intervention compared to a sham tDCS + MBRP group. We will use maximum likelihood estimation for all analyses, which provides the variance-covariance matrix for all available data and is the preferred method for estimation when some data are missing. Variables associated with missing data and those used in randomization (gender, age, treatment history) will be covaried in all analyses.

**Aim #1: Efficacy Analyses.** All assessment data will be analyzed for outliers and missing cases to detect any bias that might result from differential attrition. The efficacy of active tDCS + MBRP versus sham tDCS + MBRP will be examined using a generalized linear mixed model with drinks per drinking day at the end of treatment and follow-up as the primary outcomes. We hypothesize active tDCS will be associated with significantly larger reductions in drinks per drinking day following treatment, as compared to sham tDCS. Interim analyses to compare sham versus active tDCS treatment efficacy will be conducted in February 2017, after a sufficient number of subjects have been treated, and at the time of submitting our annual progress report to NIH, which will occur in June 2017.

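### With a fixed 2-month look-back, about 21-37 of 60 days scored at end of treatment precede session 1 in twice-weekly groups, against 0-11 in weekly groups

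*Combined protocol and SAP*

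**What the plan says.** All references are to the combined protocol and SAP.

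- **Outcome window** (V. Data Collection Procedures, Primary Drinking Outcome): "A 2-month assessment window will be used at each of the time-points". The Form 90 "gathers daily calendar-based alcohol and illicit drug use data", so each drinking day carries a date.
- **Schedules** (Procedures & Interventions, MBRP + tDCS Sessions): "we will run groups either twice per week for four weeks or once per week for eight weeks". Both schedules give up to eight sessions.
- **Post-treatment visit** (Post-Treatment Assessment): "up to two weeks after final tDCS/mindfulness session".
- **Follow-up visit** (Follow-Up Assessment): "At 2 months following completion of MBRP+tDCS, participants will complete the assessments listed in Table 1".
- **Primary outcomes** (II. Data Analysis/Statistical Considerations, Aim #1): "drinks per drinking day at the end of treatment and follow-up as the primary outcomes".
- **Covariates** (same section): predictors of missing data, and "those used in randomization (gender, age, treatment history) will be covaried in all analyses". Schedule is not named.
- **Arms within groups** (V. Data Collection Procedures): "All tDCS sessions will be double blinded with active and sham tDCS participants within all groups".

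No section starts the scored window at session 1 or scales it to the length of the course.

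**The concern.** A four-week course plus a short gap to the interview is well under two months, so a two-month look-back must reach into the time before treatment. An eight-week course nearly fills the window. The same variable therefore describes different periods under the two schedules.

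Days before session 1 cannot carry an effect of the eight-session course. The only earlier stimulation is a baseline session of under ten minutes. Drinks per drinking day also averages over drinking days only. A participant who stops drinking at session 1 would, in a window that reaches back further, be scored entirely on drinking from before treatment. The clearest responders are therefore described worst.

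At stake is what the end-of-treatment estimate means. It also affects the comparison with follow-up: a diluted first estimate beside an undiluted second one could be misread as delayed onset or a growing effect.

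**Working it through.** The plan gives no figure for pre-treatment days, so there is none to reproduce.

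**Inputs**
- Window W = 60 days ending on the interview day. This is an assumption, because the plan gives neither the day count nor the end-point; 59-62 days were also tried.
- Days from session 1 to session 8, twice weekly: S = 3 × 7 + g, where g is the number of days between the two sessions in a week. The plan does not give weekdays. Taking g = 2-4 gives S = 23-25.
- Weekly: S = 7 × 7 = 49.
- Gap from last session to interview: L = 0-14 days (Post-Treatment Assessment).

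**Step 1. Days before session 1 = max(0, W − S − L)**

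| Schedule | Most | Fewest | Share of window |
|---|---|---|---|
| Twice weekly | 60 − 23 − 0 = 37 | 60 − 25 − 14 = 21 | 35-62% |
| Weekly | 60 − 49 − 0 = 11 | 60 − 49 − 14 < 0, so 0 | 0-18% |
| Twice weekly, nominal 28 days | 32 | 18 | 30-53% |
| Weekly, nominal 56 days | 4 | 0 | 0-7% |

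A window of 59-62 days moves each non-zero count by −1 to +2 days. The contrast between schedules remains.

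**Step 2. Share of the drinking days averaged.** Let w be the share of window days before session 1 and r the drinking frequency after session 1 relative to before. The pre-session share of drinking days is w / (w + (1 − w)r).
- r = 1 (frequency unchanged): 35-62% twice weekly, 0-18% weekly.
- r = 0.5 (assumed): 21/(21 + 19.5) = 52% to 37/(37 + 11.5) = 76% twice weekly; 0 to 11/(11 + 24.5) = 31% weekly.

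**Step 3. Frequency changes equally in both arms.** Randomisation makes pre-session drinking equal on average. The arm difference in drinks is then multiplied by one minus the share in Step 2. Twice-weekly groups keep 38-65% of the on-treatment difference at r = 1 and 24-48% at r = 0.5. Weekly groups keep 82-100% and 69-100%.

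**Step 4. Frequency falls more on active (illustrative values).** Take 36 days before session 1 and 24 after (S = 24, L = 0). Before session 1 both arms have 8 drinks on 60% of days, which is 21.6 drinking days and 172.8 drinks. Afterwards active has 6 drinks on 20% of days (4.8 days, 28.8 drinks) and sham has 7 drinks on 60% of days (14.4 days, 100.8 drinks).
- Active: (172.8 + 28.8) / (21.6 + 4.8) = 201.6 / 26.4 = 7.64.
- Sham: (172.8 + 100.8) / (21.6 + 14.4) = 273.6 / 36 = 7.60.

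The on-treatment difference of 1 drink in favour of active becomes 0.04 in favour of sham.

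**Step 5. Follow-up.** A 60-day window ending two months after the last session begins at about that session. Session 1 is at least 23 days earlier on either schedule, so no pre-session days enter.

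**The case against.** **Baseline adjustment may repair this.** Where the pre-session days are also the baseline days, adjusting for baseline removes their shared noise and may restore power. It works less well after a wait for a group, which exclusion criterion 12 contemplates. This stands for power. It does not stand for the estimate, because adjustment does not rescale the arm difference, which keeps the multiplier in Step 3.

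**The scoring syntax is not shown.** The data management section says that syntax from earlier studies will produce the summary variables, and it might trim the window. That is possible, but the only stated rule is a 2-month window at each time-point, and unseen code does not override it.

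**The day counts rest on assumptions.** This stands. Weekdays, the length of two months in days and the window's end-point are all unstated, so the ranges are conditional. No variant tried removes the contrast.

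**Mixed groups protect the comparison.** A reader might infer that neither arm can be favoured because every group contains both. Mixing does stop schedule from being tied to arm. It does not stop pre-session days from weighing more in whichever arm cuts its drinking days more, as Step 4 shows.

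**Hypothesis 1 concerns drinking after treatment, and scoring from session 1 includes days during an incomplete course.** This is true, but the full window already contains those days in twice-weekly groups, and nearly all of them in weekly groups. The change removes only days that cannot reflect the course.

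**Conclusion.** The point holds for the end-of-treatment primary outcome. On the stated assumptions, 35-62% of the scored days precede treatment in twice-weekly groups and 0-18% in weekly groups. The outcome is a mixture whose make-up depends on schedule.

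Three stronger readings are tempting, and the documents do not support them:
- **A definite loss of power or a required increase in sample size.** The proportion of twice-weekly groups is not stated. The pilot effect of d = 0.64 at post-treatment may already contain the same dilution, since the pilot's window and schedule are not given. Baseline adjustment may also recover some or all of the loss. The loss against plan could be nil.
- **A guaranteed shift towards zero.** That direction needs drinking frequency to change equally in both arms. With unequal change the distortion can be larger or reverse the sign; the reversal in Step 4 shows that this can happen and is not a forecast.
- **Contamination of both primary outcomes.** Follow-up contains no pre-session days.

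The day counts are well supported within their ranges. The effect on the trial's result cannot be quantified from the documents.

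**What to change.** **Change**
1. Keep the 2-month Form 90 interview at every time-point, and both group schedules.
2. Score end-of-treatment drinks per drinking day only from days on or after session 1, up to the post-treatment interview. For anyone who never attends, use the group's scheduled first session date.
3. Report the full 2-month window as a sensitivity analysis.
4. Pre-specify how participants with no drinking days in the scored window are handled, with the alternative handling as a sensitivity analysis. Scoring them 0 counts abstinence as a value; leaving them missing drops the best responders.

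This should be settled before the first comparison of the arms. A covariate for schedule is optional: it adjusts means and does not correct the dilution.

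**Cost**
- Only SAP wording and scoring syntax change, because the data are already daily.
- Twice-weekly participants contribute about 23-39 days (28-42 with nominal courses) and weekly participants 49-60, so window length still differs by schedule.
- The twice-weekly score is noisier. Let k be the ratio of day-to-day to between-person SD and n the number of drinking days; the SD ratio is √[(1 + k²/n kept) / (1 + k²/n full)]. With assumed values at the noisy end (k = 2, drinking on 20% of days, 23 days kept), n is 4.6 against 12, giving √(1.870/1.333) = 1.18, a rise of 18%. If frequency also halves after session 1, n is 2.3 against 9.7, giving √(2.739/1.412) = 1.39, a rise of 39%.
- More participants have no drinking days. With independent days at a 5-10% drinking frequency (assumed), the proportion is 0.90²³ = 9% to 0.95²³ = 31% with 23 days kept, and 2-14% with 39.

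No net gain in precision is claimed, because these figures rest on assumed inputs and the noise calculation leaves out participants with no drinking days. The case for the change is that the outcome then measures drinking after treatment has begun.
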